9.4.2 Secondary outcomes

Aim 2: Quantify the effects of vaginal estrogen on symptoms of overactive bladder and urinary incontinence (**Subaim 2a**) and sexual function and dyspareunia (**Subaim 2b**) using validated questionnaires at regular intervals (Fig.3, Table 2) and assess for differences in rate of postoperative cystitis (**Subaim 2c**), and symptomatic vulvovaginal atrophy (**Subaim 2d**)

TABLE 2. Questionnaires Description

Pelvic Floor Distress Inventory (PFDI-20) ⁷³ (Aim 2a)	There are 3 scales (urinary, POP, and colorectal-anal symptom distress inventories) including questions about incomplete bladder emptying, urinary frequency, urgency, and urge- and stress-associated incontinence
Pelvic Floor Impact Questionnaire (PFIQ-7) ⁷³ (Aim 2a)	3 scales measure disease-specific impact on QoL (Incontinence, POP, and Colorectal-Anal) with questions about effect on physical activity, social activities, and emotional health.
Pelvic Organ Prolapse/Urinary Incontinence Sexual Function Questionnaire (PISQ-IR) ⁷⁴ (Aim2b)	Specifically assesses the impacts of PFDs (urinary incontinence and POP) on sexual health and includes questions quantifying sexual desire, arousal, orgasm, satisfaction, and pain associated with intercourse.
SF-12	Validated, commonly-used QoL questionnaire assessing overall mental and physical health
Patient Global Impression of Improvement & Severity (PGI-I, PGI-S) ⁷⁰	1-question tools validated for urinary incontinence and modified for POP. Assess overall impression of resolution of symptom bother and symptom severity related to POP.

Subaim 2a (changes in overactive bladder symptoms) will draw from the relevant questions on from the PFDI-20 and PFIQ-7. Information on stress urinary incontinence will stem from the relevant questions (PFDI-20 and PFIQ-7) completed at baseline and at the Pre-op visit.

Use of CE cream and conversion of inelastic, avascular, thin epithelium to a thicker, well-rugated epithelium corresponding to decreased pH could reduce the incidence of postoperative cystitis (**Subaim 2c**), which is common after genitourinary surgery (14% after USLS, defined by +culture within 1mo post-op)⁸⁴. This study will use a more liberal definition of post-op cystitis to include any prescription of antibiotics (culture-driven or empiric) for cystitis symptoms in the first postoperative month.

Atrophy (and its resolution, **Subaim 2d**) will be queried at baseline, Pre-op, 6- and 12-mo postoperatively using standardized questions about bother related to vaginal dryness, irritation/itching, soreness/pain, discharge, and dyspareunia (if sexually active); these symptoms are each scored as 1=not at all, 2=somewhat, 3=moderately, or 4=quite a bit bothersome.⁷⁵ The most bothersome symptom (MBS) is also queried. On exam, a modification of the vaginal health composite score⁸⁵ will have the examiner grade vaginal mucosal dryness, pallor, presence of rugae, and presence/absence of petechiae. The vaginal maturation index objectively categorizes percent of superficial, intermediate, and parabasal cells to be used as an index of patient adherence and to examine for correlation with symptom bother from other PFDs.

Aim 3: Quantify histomorphology and connective tissue homeostasis of the vaginal wall in postmenopausal women with symptomatic prolapse undergoing surgical repair with or without pre- operative intravaginal estrogen therapy.

Aim 3 Methodology:

a. Vaginal wall biopsy: Standardized full-thickness anterior apical vaginal wall biopsies will be obtained from all consenting participants at the time of prolapse repair. Biopsies from secondary clinical sites will be received in RNA preservative (RNAlater®). Although this buffer is excellent for preservation of RNA and facilitates dissection of biopsy material into various tissue components (e.g., muscularis from mucosa) and fixation of tissues after receipt, immunoblot analysis and enzymes assays are not possible. Thus, tissues obtained from only the primary site (UTSW) will be used to quantify protein and enzyme activity in addition to molecular analysis. Biopsies from all sites will be used for molecular and histopathology analyses.

b. Rationale for study of candidate genes and proteins in the vaginal wall: The pelvic viscera are supported anatomically by the levator ani muscle complex and connective-tissue attachments of the pelvic organs (aka the “endopelvic fascia”).⁸⁶ The vagina’s support is commonly divided into apical (Level I), mid- (Level II), and distal (Level III) regions.⁸⁷ The cardinal and uterosacral ligaments (Level I) have long been regarded as integral to the system of support of the pelvic organs⁸⁸, and despite the name *utero*-sacral, this ligament interlaces and is contiguous with the upper vagina in more than two-thirds of women.^{89,90} Further, the connective tissue sheet enveloping the vagina suspends it to the levator ani via the arcus tendineus fascia pelvis (Level II).⁹¹ Dysfunction or disruption of one or more of these muscular, ligamentous, or connective tissue components leads to loss of support and, eventually, to POP. Importantly, the fibromuscular layer of the vaginal wall coalesces and is contiguous with the endopelvic fascia, and, thus, plays a role in the suspension of the vagina to the pelvic floor musculature. Work from the [name] laboratory and others provides compelling evidence that the vaginal muscularis is abnormal in women with prolapse compared with age- and parity-matched asymptomatic controls with respect to smooth muscle proteins⁹², cellular composition^{93,94}, ultrastructural abnormalities, and protease activity.⁹⁵ Findings from other laboratories⁹⁶⁻⁹⁹, together with the known association between inherited elastinopathies and POP¹⁰⁰⁻¹⁰², suggest that defective collagen or elastic fiber assembly (or increased degradation) is a primary and pivotal event in the pathophysiology of POP.

Synthesis and assembly of collagen and elastin.

- a. Relative levels of mRNA for collagen types *1 α 1*, *1 α 2*, & *3*, *tropoelastin*, *LOX*, *LOXL-1*, and *TGF β* will be quantified using qPCR and gene-specific primers which have been validated in the [name] laboratory.
- b. Immunoblot analysis for Collagen types I and III will be conducted using samples from CE- and placebo-treated women and compared with expression in vaginal tissues from premenopausal women with normal vaginal support and premenopausal women with prolapse (samples in our existing biorepository). Likewise, levels of tropoelastin, LOX, LOXL-1 and fibulins-3 and -5 will be quantified in urea-extracted matrix fractions from the mucosa (lamina propria + epithelium) and muscularis. This analysis will allow us to determine (i) the effect of menopause on expression of these matrix proteins in the vaginal wall, and (ii) if vaginal estrogen alters the connective tissue matrix.
- c. Collagen and elastin content will be analyzed using hydroxyproline and desmosine assays, respectively. The distribution of collagen (newly synthesized, denatured, or mature) will be analyzed in fractions of tissue extracts (i.e. supernatant of NaOH

- extraction as newly synthesized uncrosslinked or weakly crosslinked collagen; extraction of insoluble residue with 0.5 M acetic acid in which the supernatant represents denatured collagen and insoluble residue as crosslinked collagen).
- d. Histomorphology will be analyzed in detail. Specifically, we will use Hart's staining to analyze elastic fiber morphology and content¹⁰³, picrosyrius red stain to analyze collagen morphology and content¹⁰³, thicknesses of epithelium, lamina propria, and muscular wall, and CD68 immunostaining to quantify macrophages. Macrophages may be important in POP since our pilot data indicate estrogen-induced downregulation of MMP12 (i.e., human macrophage elastase) in the vaginal wall.

Matrix degradation. We hypothesize that certain collagenases (MMP-1 and -13), trypsinogens (PRSS3)¹⁰⁴, and elastases (MMP-2, -9 and -12) and their respective inhibitors may be regulated by vaginal estrogen. We propose that postmenopausal women with POP will respond to estrogen therapy with decreased levels of MMPs (collagenases and elastases), decreased NTx (elastin degradative product) and decreased collagenase associated with collagen/elastin deposition relative to placebo-treated controls. Further, we propose that *failure* of reconstructive surgery will be associated with increased markers of collagenase and elastase activity.

- a. Collagenase activity will be determined using collagenase activity assays with FITC-labeled soluble type-I collagen as substrate (Chondrex Inc. Redmond, WA). MMP-9 and MMP-2 will be analyzed using quantitative gelatin zymography and endogenous active MMPs (-2,-9, -13) will be measured using active MMP fluorescent immunoassays (R&D Systems).
- b. The serine protease, PRSS3, will be analyzed using casein zymography, IHC, and immunoblot analysis.
- c. Levels of cross-linked collagen-type I N-telopeptides (NTx) will be used as an index of collagen degradation in biological fluids and tissues. NTx will be quantified in homogenates of mucosa and muscularis using competitive inhibition enzyme linked immunosorbent assays normalized to total protein (Oswteomark NTx Urine, Wampole Laboratories, Princeton, NJ).
- d. A cassette of signature protease inhibitors (cystatin C, SLPI, TIMP-1 and -2, and elafin) will be analyzed using qPCR and immunoblot analysis.
- e. Elastase activity in vaginal muscularis and mucosa will be determined using BODIPY-FL-labeled DQ elastin conjugate that is highly labeled so that the fluorescence signal is quenched until enzymatic digestion yields highly fluorescent fragments (Molecular Probes). We have experience with preparation of vaginal tissue for these assays.

Vaginal smooth muscle.

- a. Relative levels of mRNA for smooth muscle α actin will be used as a marker for smooth muscle cells and myofibroblasts. Smooth muscle myosin heavy chain and h- and l-caldesmon will be assessed as markers for the fully differentiated smooth muscle phenotype.⁹²
- b. Immunoblot analysis for myosin heavy chain, caldesmon, and α actin will be conducted using samples from CE- and placebo-treated women and compared with expression in vaginal tissues from premenopausal women with normal vaginal support and others with prolapse (samples in our biorepository).⁹²

- c. Histomorphology will be analyzed in detail. Specifically, we will use immunostaining for α actin and smooth muscle myosin heavy chain to analyze smooth muscle morphology and content.^{93,94}

Molecular profile of vaginal wall tissues (all clinical sites). High quality RNA from tissue samples obtained in this trial will facilitate a comparative analysis of gene expression related to matrix synthesis and degradation. It is not possible to analyze hundreds of genes involved in these pathways especially in ~392 (196 ea of muscularis and mucosa) tissues. We, therefore, choose to quantify mRNA levels of select genes related to matrix synthesis and degradation to determine a molecular profile of estrogen action in vaginal tissues.

Analysis of tissues from women enrolled in our pilot trial indicated that, of 7 genes important in collagen and elastin synthesis, the magnitude of estrogen-induced change was greatest and most consistent in *Col1a1* (6-fold). With increased numbers of subjects, we expect that vaginal estrogen will also result in increased *LOX* gene expression (which correlates with enzyme activity) in the vaginal muscularis. Hence, we will utilize qPCR to measure relative levels of *LOX* and *Col1a1* mRNA as markers of collagen synthesis in all tissue samples from this trial. *Col3* and *tropoelastin* will be used as potential negative controls and at least two housekeeping genes will be used as normalizers (*h36B4* and *GAPDH*).

Our pilot trial indicated that mRNA levels for serine protease and MMP inhibitors were not regulated by vaginal estrogen. The single exception was the serine protease inhibitor, *α 1-antitrypsin*, which tended to be increased in mucosal samples from women treated with estrogen ($P=0.27$). In contrast with protease inhibitors, 2 protease genes (*MMP1* and *MMP12*), were significantly decreased in tissues from CE-treated women, and MMP9 activity was also downregulated dramatically in CE-treated women. Thus, *MMP1*, *MMP12*, and *α 1-antitrypsin* will be quantified in all tissue samples using *MMP2* and *TIMP1* as negative controls.

This molecular profile will determine if collagen synthesis and degradation is regulated by vaginal estrogen. Nonetheless, *MMP1* gene expression remained elevated in 1 of 7 mucosal samples from women treated with CE. As shown in Fig.2 of this protocol, MMP9 was not universally downregulated in women treated with CE. These studies illustrate that estrogen-induced downregulation of matrix proteases may vary significantly among subjects. We will also quantify ER α and ER β mRNA to test whether responses correlate with expression of estrogen nuclear hormone receptors in the vaginal wall and will use the well-known estrogen-responsive gene, *VEGF*, as an index of estrogen action in these tissues.

Future Aim.

From those participants consenting to an optional additional blood draw, 5mL (1 teaspoon) of whole blood will be obtained at baseline and stored in a typical yellow-top tube. This will be stored for possible future DNA analysis such as genetic analyses looking for genetic predictors of surgical success or failure.

9.5 Data Analyses

Aim 1. The **primary outcome** will be analyzed according to the assigned treatment group (modified intention-to-treat): i.e., all participants that are randomized *and* undergo a surgical prolapse repair *and* have at least one postoperative assessment will be analyzed according to their randomized assignment group. All eligible subjects who consent to the study and are enrolled will be available for analysis of baseline characteristics, and those that are randomized and use their study drug will be monitored for adverse events, but they must meet the additional qualifications above (i.e., undergo surgery and have a postoperative assessment) to be analyzed for the primary study outcome. At baseline, continuous measures will be compared between groups with Student's t-test and chi-square (or Fisher's exact test) for categorical measures. Scores from repeated surveys are continuous outcomes data and will be analyzed using repeated measures analysis of variance. We will test for interactions between time effect and treatment effect. For categorical data (e.g. prolapse stage), the analysis will be by categorical data modeling using weighted least squares and mixed logit models, with cross-sectional assessments (at specific time intervals) by chi-square. For missing follow-up points there are two possible approaches: (i) if there are few missing follow-up points, then their values may be imputed through multiple imputation methods, in which case repeated measures analysis of variance may be used following multiple imputation; (ii) more likely, we will make time a random effect and a mixed effects model with repeated measures will be applied. Time-to-event or event-free-time will be analyzed using survival methods to include the log-rank test and Cox regression. For measures that may not be assumed normal, the data will be transformed using a rank transformation prior to analysis.

In accordance with NIH policy, we will include an analysis of the intervention effect (CE cream) performed by racial/ethnic subgroups, recognizing that the analyses will not have high statistical power for detecting clinically meaningful differences between races/ethnicities.

Aim 2 Outcomes. As above, continuous scores from repeated surveys will be analyzed using repeated measures analysis of variance with appropriate corrections made, as necessary, for missing data.

Subaim 2a & 2b. Assuming a baseline UDI-6 score (*obtained from the PFDI-20*) of 7.90 ± 1.91 for the stress-incontinent subpopulation of IMPROVE (expected to be at least 60%, or 67 participants per study arm)¹⁰⁵, in order to demonstrate a clinically meaningful improvement (decrease) of $0.5(\text{SD})^{106}$ to 6.95 ± 1.91 using CE cream from baseline to time of surgery (preop), with 80% power and $\alpha 0.05$, 65 participants are needed per arm. Further, to demonstrate an improvement in a baseline IIQ-7 score (*obtained from the PFIQ-7*) of 9.67 ± 7.14^{105} to 6.12 ± 7.1 , 64 participants are needed per arm (Subaim 2a). Similarly, to find a clinically important improvement (increase) in overall PISQ-12 score from baseline 25.0 ± 4.95 (women with prolapse¹⁰⁷) to 27.48 ± 4.95 at preop (or any postoperative time point), 64 participants are needed per arm (Subaim 2b). Thus, enrollment goals designed to address the primary aim (Aim 1) are sufficient to address these important secondary aims.

Because midurethral slings and anticholinergic or beta-3 agonist medications are not excluded in study participants, these other interventions will clearly impact upon

incontinence rates and will be controlled for in statistical comparisons between the two groups. Gross estimates of overactive bladder in the 2 groups will also be assessed by rates of anticholinergic or beta agonist use, as medication history will be queried at each patient encounter. Modest improvements in *stress* and overall urinary incontinence will be assessed from baseline to Pre-op (i.e. approximately 6-8wks local estrogen) using the relevant PFDI-20 and PFIQ-7 questions (see above Analyses) at both time points.

Subaim 2c. Proportions of participants with postoperative cystitis will be compared using chi-square. Using the liberal definition of post-operative cystitis to include any patient prescribed antibiotics for cystitis symptoms, this study will have sufficient power to demonstrate an improvement from a 22% cystitis rate to 10% (80% power, α 0.05). The postoperative “MedSurg” history form (**Form 15**) queries whether there has been any interval occurrence of urinary tract infection (Item B4) and whether symptoms were treated empirically (i.e., no urine culture) or if culture-proven.

Subaim 2d. Comparisons of vaginal maturation index and atrophy symptoms will use analysis of covariance, with treatment and study center as factors and baseline values as the covariate.

Aim 3 Outcomes: If there is 10% loss of patients from randomization (baseline) to surgery, there will still be 100 patients per arm eligible for the standardized intraoperative apical anterior vaginal wall surgical biopsy. Our pilot trial (Section 2.2a, *Humans*) indicates sufficient power to determine 2-fold differences in collagen subtypes and MMP activity using tissues from UTSW. Further, with ~42 samples from UTSW (21 in each group), this will provide 80% power to also detect 2-fold differences in LOX protein and mRNA expression. All Aim 3 outcomes of interest (e.g. histological wall thicknesses, qPCR-determined relative mRNA levels, collagen subtypes and elastic fiber content, collagenase and protease activity) will be summarized using the following statistics: mean, standard deviation, median, minimum and maximum. Additionally, because most biomarkers are not normally distributed, the geometric mean and standard deviation based on natural log transformed values will also be calculated. Summaries will be constructed by treatment group (CE vs. placebo) and comparisons conducted using 2-tailed Student’s *t*-tests comparing natural log transformed levels. Because this translational study (Aim 3) is considered to be descriptive and a relatively large number of markers are being considered, all p-values will be presented without adjustment for multiple comparisons and should be interpreted accordingly. We will correlate any treatment-group differences in vaginal wall or smooth muscle histomorphology, ERs, collagen gene expression, and protease downregulation with *clinical outcomes*, namely, objective or subjective “success” as outlined in Aims 1 and 2.

Ideally, CE cream application will support an improvement in prolapse recurrence success/failure rates 1y postop, but even if CE cream has a null or non-significant effect, the entire population will be divided into prolapse repair failures (*cases*) and successes (*controls*), and, controlling for CE cream exposure, univariate comparisons will be made of the continuous outcomes from Aim 3 (2-tailed Student’s *t*-tests). Those variables that attain a significance level of 0.1 or less in univariate analyses will be considered jointly in a multivariable backward stepwise logistic regression model. An accepted “rule of thumb”

is that one needs 10 events (i.e. 10 cases of prolapse repair failure) for each predictor added to the model (i.e., for each degree of freedom).^{108,109} If a total of 67 cases are identified (i.e., 40% repair failure in 222 participants and 25% patient loss), this would be sufficient to analyze up to at least 7 variables in the multivariable model. Thus, we will identify important biomarkers that predict greater risk for failure of native tissue repair. These findings could theoretically be used to tailor the choice of surgical approaches for these higher-risk patients.

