Design: Randomized, double-blind, placebo-controlled trial of pre- and postoperative intravaginal estrogen therapy in 222 postmenopausal women with symptomatic prolapse undergoing a standardized surgical repair using native tissue.

Primary outcome: prolapse recurrence as defined by a composite of objective prolapse beyond the hymen, subjective/symptomatic prolapse (feeling of a bulge or *no change* or *worse* on the patient's global impression of improvement), or retreatment (e.g., reoperation or pessary use) assessed 1 year postoperatively. *Time to failure* will be compared in the two groups.

Important secondary outcomes assessing for changes in overactive bladder and urinary incontinence symptoms will be made by comparing symptoms (validated questionnaires) from Baseline to Pre-op/time of surgery. Aim 3 (see above, histomorphology, connective tissue studies) will be assessed from full thickness anterior apical vaginal wall biopsies taken at the time of surgery.

Interventions and Duration

Intervention: 1g conjugated estrogen (CE) cream (Premarin®, Pfizer Inc.) given nightly for 2 weeks then twice-weekly to complete planned 6-8 weeks (5 weeks minimum) therapy before a standardized uterosacral or sacrospinous ligament suspension transvaginal prolapse repair surgery. Those with a uterus will undergo concomitant total vaginal hysterectomy first. Twice-weekly CE cream application is then resumed upon discharge and continued for 1 year postoperatively.

Comparator: placebo vaginal cream, same schedule

Duration: The primary outcome of prolapse recurrence is assessed at one year postoperatively with continued surveillance of participants until 3 years postoperatively.

Sample Size and Population

Total sample size: N=222; 111 per treatment group

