6.2.2 Enrollment, Baseline, and/or Randomization

Enrollment

In this study, a single informed consent will encompass both screening and study procedures (as screening procedures are a part of routine care). Enrollment and randomization will occur on the same day all screening criteria are met and the individual agrees to participate. This enrollment/randomization date will be captured on a case report form at the *Baseline assessment*.

Baseline Assessments

- Contact Information (**Form 01**): name, address, phone, email data from patient and an alternative contact. Confirm patient's assent to being contacted by text and/or email.
- Demographics (**Form 02**): racial/ethnicity data and type of health insurance payer
- Medical History (**Form 03**): smoking history, confirmation of postmenopausal status, hysterectomy status, and assessment for history of recurrent urinary tract infection, diabetes, connective tissue disease, and various medical conditions
- Baseline Physical Exam (**Form 04**): gather height, weight, Pelvic Organ Prolapse Quantification (POP-Q) exam, uterine size, levator muscle tone and strength, investigator assessment of vaginal atrophy, and vaginal maturation index (VMI) specimen collection (see below).
- Medication Review (**Form 05**): list all medications related to treatment of incontinence and overactive bladder
- Pelvic Floor Disorder (PFD) Questionnaires (**Form 10**): *see description above in 6.1*
- Patient Global Impression of Severity (PGI-S) (**Form 11**): 1-question tool validated for urinary incontinence and modified for POP. Assesses overall impression of symptom severity related to POP.
- Vaginal Maturation Index (VMI): See also Section 5.4. A standard plastic spatula (similar to those used for a Pap smear and readily available in any gynecology clinic) will be used to sample the upper vaginal walls for 15-30 seconds. The spatula will be swirled in a ThinPrep® container (labeled with a preprinted barcode label with a Specimen ID linked with the participant's Subject ID number), which is then stable when stored at room temperature or 4°C and shipped with cold packs in a cold shipping box for storage at UTSW.
- Blood serum collection: Blood will be drawn into a standard red top tube. 5mL (1 teaspoon) is gathered to assess baseline estrone (E1) and estradiol (E2) levels.
 - Tube: Red top glass, no additive, no clot activator with uncoated interior, vacutainer tubes (BD366430 - 16 x 100 mm x 10.0 ml)

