9 STATISTICAL CONSIDERATIONS

9.1 General Design Issues

A large simple trial (randomized, controlled) design was selected to evaluate for possible superiority of vaginal estrogen cream use compared to placebo. The primary outcome is a comparison by treatment group of time-to-failure of the prolapse repair at 1 year after surgery with "failure" defined by the *any* of these outcomes occurring:

- Recurrent prolapse beyond the hymen of the anterior or posterior vaginal wall *or* apical descent >1/3 into the vaginal canal based on continuous measurements of the Pelvic Organ Prolapse Quantification (POP-Q)⁷¹ examination
- Report of any symptoms of bulge: “yes” to question #3 of the Pelvic Floor Distress Inventory, “Do you usually feel a bulge or something falling out that you can see or feel in your vaginal area?” or *no change* or worse on the Patient Global Impression of Improvement (PGI-I).
- Retreatment of prolapse with either pessary or surgery

The null hypothesis for this study is that 12 months following transvaginal native tissue repair for prolapse with or without preoperative and continued postoperative local estrogen treatment, women will have the same rate of recurrent prolapse. The current definition of success in a surgical trial used by NICHD’s Pelvic Floor Disorders Network (PFDN) is this same composite of no prolapse beyond the hymen, no symptomatic recurrence, and no retreatment.^{81,82}

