9.2 Sample Size and Randomization

The literature reports failure by the above definition occurring in ~40% of patients with a native tissue USLS (i.e., ~60% “success”).⁶⁹ A 2-sided logrank test with an overall sample size of **188 subjects** (94 each group) achieves 80% power at a 0.05 significance level to detect a hazard ratio of 0.5188 when the proportion of those "surviving" (i.e. "successes") in the control group is **65% compared to 80%** in the treated group, **measured at 1 year**. This presumes the accrual pattern across the study time period (3 years of accrual) is uniform. This N=188 already accounts for **25%** either lost to follow-up *or non-adherent to study cream* in the control and treatment groups. Allowing for an additional **15% loss of participants** from baseline to surgery, **222 total participants** are needed.

Potential problems & alternatives:

Differences in baseline characteristics between the groups may occur by chance, but we will mitigate that risk by stratifying by clinical site, hysterectomy status, and duration since menopause (<10y & ≥10y).

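### Baseline POP-Q is recorded for every woman but is not a prespecified covariate in the primary time-to-failure analysis; naming it would cost little and gain a little

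*Combined protocol and SAP*

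**What the plan says.** Section 9.5 (Aim 1) covers the survival analysis in one sentence: "Time-to-event or event-free-time will be analyzed using survival methods to include the log-rank test and Cox regression". It does not say which of the two is the primary test, whether the log-rank test is stratified, or what the Cox model contains. Section 9.2 sizes the trial on a test without covariates: "A 2-sided logrank test with an overall sample size of" 188, which "achieves 80% power at a 0.05 significance level to detect a hazard ratio of 0.5188".

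Baseline POP-Q will be on file for everyone. The baseline examination form in Section 6.2.2 is to "gather height, weight, Pelvic Organ Prolapse Quantification (POP-Q) exam", and the Schedule of Evaluations (Table 1) marks POP-Q at baseline. In Section 9.1 the anatomic route to failure is "based on continuous measurements of the Pelvic Organ Prolapse Quantification" examination. The other two routes are symptoms (a bulge, or a PGI-I rating of no change or worse) and retreatment.

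Randomisation is stratified by site, hysterectomy status and years since menopause (Sections 9.2 and 9.2.1). Section 9.2 offers that stratification as its protection against chance differences at baseline. A baseline value is a named covariate only for Subaim 2d.

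**The concern.** Section 4.1 sets a floor of stage 2 for prolapse and no ceiling, so baseline severity can differ between women. If it predicts recurrence, a test that ignores it has less power than one that uses it. A chance difference between arms in baseline prolapse would also pass straight into the treatment estimate, because the stratification does not cover prolapse severity.

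The open wording matters too. Section 9.5 plans baseline significance tests between the groups but does not say what follows if POP-Q differs. With Cox regression planned and no covariates listed, the choice to adjust could be made after the data are seen.

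**Working it through.** **Inputs from the plan.** Two-sided 5% log-rank test, 80% power, hazard ratio 0.5188, one-year success of 65% and 80%, 94 per group, 25% loss or non-adherence already inside 188, and 15% loss before surgery (all Section 9.2). On accrual: "This presumes the accrual pattern across the study time period (3 years of accrual) is uniform". **Not in the plan:** the prognostic strength of baseline POP-Q. I take hazard ratios per SD from 1.0 to 2.0 as an assumed range.

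**1. The plan's own figure.**
- ln 0.80 / ln 0.65 = 0.518, close to 0.5188.
- Events needed: 4(1.960 + 0.842)² / (ln 0.5188)² = 73.
- With exponential failure, 3 years of uniform accrual and one further year, follow-up runs from 1 to 4 years. The failure probability is 1 − (e^(−λ) − e^(−4λ))/(3λ), with λ = −ln(one-year success). This gives 0.635 for control and 0.417 for treated, mean 0.526.
- 73 / 0.526 = 139, and 139 / 0.75 = 186, against 188 stated.
- 188 / 0.85 = 221.2, so 222, as stated.

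**2. The same design at a fixed 12 months.** The mean failure probability is (0.35 + 0.20)/2 = 0.275, so 188 women give 51.7 events. Power is Φ(√(51.7/4) × 0.656 − 1.960) = Φ(0.399) = 0.655. This is why the 12-month powers below sit near 63% and not 80%.

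**3. Effect of adjustment, 94 per arm, 12 months.** 5,000 simulated trials per scenario, exponential failure times, marginal success held at 65% and 80%, Wald test from Cox models without and with one standardised linear covariate:

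| Assumed HR per SD | Unadjusted | Adjusted | Change (points) |
|---|---|---|---|
| 1.0 | 63.3% | 63.6% | +0.3 |
| 1.3 | 62.3% | 63.2% | +0.9 |
| 1.5 | 64.3% | 66.2% | +1.9 |
| 2.0 | 63.4% | 70.1% | +6.7 |

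**4. Other settings.** A second simulation, 3,000 trials per cell, Monte Carlo error about 0.9 points per figure. The 141 is 188 × 0.75. Cells show power (%) for log-rank / unadjusted Cox / adjusted Cox:

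| HR per SD | 188 women, 12 months | 141 women, 12 months | 141 women, 1–4 years |
|---|---|---|---|
| 1.0 | 62.7 / 61.8 / 62.0 | 51.3 / 49.9 / 49.8 | 81.2 / 80.7 / 80.6 |
| 1.2 | 63.7 / 63.0 / 63.3 | 50.9 / 49.4 / 49.6 | 79.1 / 78.6 / 79.9 |
| 1.35 | 63.0 / 62.3 / 64.1 | 51.8 / 50.5 / 51.6 | 77.4 / 76.7 / 79.0 |
| 1.5 | 62.6 / 61.4 / 64.7 | 53.0 / 51.5 / 52.9 | 76.3 / 75.7 / 79.6 |
| 2.0 | 64.5 / 63.6 / 70.4 | 53.1 / 51.7 / 58.8 | 72.4 / 71.9 / 83.2 |

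The hazard ratio given the covariate moves from 0.518 (inert) to 0.490 (HR per SD 2.0), although the marginal success rates are unchanged.

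**5. Chance imbalance.** With 94 per arm, the difference in means of a standardised covariate has standard error √(2/94) = 0.146 SD, so 95% limits are ±1.96 × 0.146 = ±0.286 SD. To first order, the unadjusted hazard ratio is multiplied by 1.5^(±0.286) = 0.89 to 1.12 at an HR per SD of 1.5, and by 2^(±0.286) = 0.82 to 1.22 at 2.0.

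**The case against.** The strongest reply is that nothing in the documents shows a benefit. They give no prognostic strength for baseline POP-Q and no baseline distribution. Surgery corrects the baseline anatomy before the outcome is assessed. Only one of three failure routes uses POP-Q, and the 3- and 9-month contacts are calls without an examination. A hazard ratio of 2.0 per SD means a fourfold difference in hazard (2² = 4) between women 1 SD above and 1 SD below the mean. All of this stands, and it is why the gain must be stated as conditional.

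A second reply is that with 141 women at 12 months the adjusted Cox test gains nothing over the log-rank test for an HR per SD up to 1.5 (changes of −1.5 to about 0 points). This does not hold as an argument against the covariate. The unadjusted Cox Wald test already sits 1.3 to 1.5 points below the log-rank test in that setting, so the deficit comes from the choice of test statistic. Against the unadjusted Cox model the changes are −0.1, +0.2, +1.1, +1.4 and +7.1 points. A further paired comparison of 3,000 trials per cell gave +1.5 and +2.6 points at 1.3 and 1.5 in this setting, and −0.3 to +0.4 points over the settings tried when the covariate was inert.

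A third reply stands in full: adding a covariate to a Cox model changes nothing if the unadjusted log-rank test remains primary. It is also fair that leading-edge position does not separately capture the apical-descent criterion in Section 9.1.

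**Conclusion.** The point holds as a minor improvement. Baseline POP-Q is collected for all women and bears on one failure route, but it is neither a stratification factor nor a prespecified covariate. At 12 months with 94 per arm, adjustment is worth about 0, +1, +2 and +6.5 points of power at assumed hazard ratios per SD of 1.0, 1.3, 1.5 and 2.0. It also protects against chance imbalance in baseline prolapse, as far as a linear term captures its effect. Confidence in the size is low because the prognostic strength is assumed.

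A reader might infer more, and the documents do not support it:
- That the plan leaves POP-Q out of the analysis. Section 9.5 neither includes nor excludes it.
- That the trial is giving up a known amount of power. That depends on a figure the plan does not contain, and the gain is small unless POP-Q is strongly prognostic.
- That failure is mainly a POP-Q measurement. Symptoms or retreatment alone also count.
- That adjustment would restore 80% power. The stated 188 reproduces only with follow-up of 1 to 4 years. The shortfall at a fixed 12 months is a separate and larger matter.

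**What to change.** In Section 9.5, Aim 1, state that the primary test of treatment comes from a Cox model with baseline POP-Q leading-edge position (cm, linear) as a prespecified covariate, and that the log-rank test is supportive. Name the test statistic as well: a score or likelihood-ratio test should avoid most of the small deficit of the Wald test seen above. The same sentence can settle whether the randomisation factors enter the model.

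The cost is a wording change and one degree of freedom, with no new data. The adjusted hazard ratio is conditional on baseline POP-Q, so it need not equal the planning value of 0.5188. The text should say so, and the unadjusted hazard ratio should be reported beside it.
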